### **7.2. Overall Study Duration and Follow-Up**

The study will consist of a 28-day (+3 days) screening period for each subject, a 12-month treatment period, and a 4-month remote safety follow-up visit after the subject's last treatment injection. The end of the study for each subject will be the last study visit or the visit at which the subject discontinues from the study (before the 12-month visit). Each follow-up visit will include a 4-day window before and after the visit for completion of all assessments. The follow-up period will include efficacy and safety following treatment initiation of daclizumab. The end of the study overall will be defined as the end of the 12-month study follow-up period for the last patient. The 4-month safety follow-up visit will be conducted remotely after the 12-month study follow-up visits have been completed.

Subjects having tentative disability progression identified near the end of the core study (e.g., Month 12) will attend additional follow-up visits 12 and 24 weeks later to confirm progression.

Subjects may discontinue treatment at any time during the study, and they will be followed for an additional 4 months to collect data on safety, LFT, MS treatment, relapses, and the use of concomitant medications.

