## 4.2. Schedule of Assessments

The schedule of assessments is presented in [Table 1](#). Assessment time points include an enrollment visit, a baseline visit, and follow-up visits at Months 1, 3, 4, 6, 9 and 12. An additional safety assessment will be performed remotely 4 months after the last study treatment dose. Subjects who discontinue treatment early will still be evaluated during the safety follow-up visit (i.e., 4 months after treatment and study discontinuation). Subjects having tentative disability progression identified near the end of the core study (e.g., Month 12) will attend additional follow-up visits 12 and 24 weeks later to confirm progression.

Magnetic resonance imaging (MRI) scans will be performed at the enrollment visit (no later than 7 days prior to the first dose of daclizumab), and at Months 1, 4, 6 and 12. MRI scans will be performed under the supervision of a trained radiologist. Ad-hoc MRI scans may be performed as needed, such as in the event of a MS relapse, in order to rule out a progressive multifocal leukoencephalopathy (PML) diagnosis.

Blood chemistry and hematology assessments will be performed at baseline and at Months 1, 3, 6, 9 and 12. Hematology assessments will include a complete blood count (CBC). Liver function tests (LFT) [alanine transaminase (ALT)/ aspartate transaminase (AST)] will be done at enrollment and monthly visits. Bilirubin testing must be done together with the first AST/ALT test at the enrollment visit. Bilirubin testing must also be done if ALT/SGPT (serum glutamic pyruvate transaminase), or AST/SGOT (serum glutamic oxaloacetic transaminase)  $>3*$ upper limit of normal (ULN), since treatment must be permanently discontinued with the concomitant elevation of total bilirubin  $>2*ULN$ .

At the end of the study, liver monitoring will be done per routine clinical practice.

A safety follow-up visit at 4 months after the last dose of daclizumab provided by the study will be conducted remotely to evaluate potential delayed safety outcomes. The assessments during the additional safety follow-up period will include all safety endpoints described in [Table 1](#). Liver function tests (LFT) will be performed only if the subject is continuing daclizumab or if the subject is within 4 months since study treatment discontinuation, and monitoring is deemed appropriate by the Investigator.

CONFIDENTIAL

The information contained herein may not be used, disclosed, or published without the written consent of  

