### **9.2. Follow-Up**

Subjects will be followed-up for 12 months with assessments at Months 1, 3, 4, 6, 9, and 12. There will be a 4-month safety visit conducted remotely. The follow-up study assessments are described in Section 11.2.

Subjects having tentative disability progression identified near the end of the core study (e.g., Month 12) will attend additional follow-up visits 12 and 24 weeks later to confirm progression.

Subjects who do not receive a treatment dose for 2 or more consecutive months will continue to be followed for data collection.

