### **9.3. Withdrawal of Subjects from the Study**

Subjects must be withdrawn from the study for any one of the following reasons:

- The subject withdraws consent.
- The subject is unwilling or unable to comply with the protocol.
- The Investigator withdraws the subject from the study for medical reasons.

The reason for the subject's withdrawal from the study must be recorded in the subject's case report form (CRF).

Subjects who withdraw from the study will not be replaced.

CONFIDENTIAL

The information contained herein may not be used, disclosed, or published without the written consent of  
Biogen MA Inc.

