### **13.2. Analysis Population**

The analysis population is based on intent-to-treat (ITT), where the subjects should receive at least 1 dose of the medication during follow-up. Subjects discontinuing treatment will also be included in the analysis.

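### Follow-up after stopping daclizumab is not described consistently, so Month 12 relapse outcomes and post-stopping MRI can be lost in subjects the protocol keeps in its analysis

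*Protocol*

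**What the plan says.** Five places in the protocol bear on what happens once a subject stops daclizumab.

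- Section 7.2 says: "Subjects may discontinue treatment at any time during the study, and they will be followed for an additional 4 months". Relapses are among the data listed for that period; MRI is not.
- Section 4.2 says that subjects who stop treatment early "will still be evaluated during the safety follow-up visit (i.e., 4 months after treatment and study discontinuation"). The two events are written as one.
- Section 9.2 says: "Subjects who do not receive a treatment dose for 2 or more consecutive months will continue to be followed for data collection". It sets no end to that follow-up.
- Table 1, footnote 14, defines early discontinuation as ending study participation, not as stopping the drug.
- Section 9.3 opens its list with "Subjects must be withdrawn from the study for any one of the following reasons". The reasons are withdrawn consent, non-compliance and withdrawal by the investigator on medical grounds. Stopping daclizumab is not among them.

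On the analysis side, Section 13.2 says: "Subjects discontinuing treatment will also be included in the analysis". Sections 13.4.1 and 13.5.1 run time to relapse from first dose to first relapse or end of study. Section 13.3 generally rules out imputation. The SAP differs: Section 5.1 censors a relapse-free discontinuer at the last dosing date, while Section 5.2.2 analyses ARR over both the treatment period and the study period.

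**The concern.** A subject who stops daclizumab for good fits the wording of both 7.2 and 9.2. One section gives 4 months of follow-up without MRI; the other gives open-ended follow-up. A site cannot tell from the text whether that subject attends the later relapse visits and scans, and about 40 sites would each decide.

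The protocol's analyses need those data. It includes treatment discontinuers, and 13.4.1 and 13.5.1 provide for sensitivity analyses that exclude subjects with 2 or more consecutive missed doses. That only makes sense if the main analysis has those subjects' outcomes. The 12-month McNemar comparison is limited to subjects with relapse information, described as study completers, so a subject whose follow-up ends early drops out of it.

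Stopping is foreseeable: 10.5.1 requires permanent discontinuation for specified liver findings, and 5.1.4 reports that 5% of daclizumab subjects in the earlier active-controlled trial stopped for cutaneous events. If stopping is related to later disease activity, losing these subjects' later outcomes biases the Month 12 results.

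**Working it through.** **Inputs.** Doses are monthly from baseline to Month 11, so there are 12 possible last-dose times (Table 1, footnote 8). Follow-up after stopping is 4 months (7.2). Relapse endpoints are read at Months 6 and 12, and MRI endpoints at the same months (6.1). Table 1 schedules relapse assessment at baseline, Months 1, 3, 6, 9 and 12, the safety visit and the early discontinuation visit. It schedules MRI at enrollment and Months 1, 4, 6 and 12, with none at the safety or early discontinuation visit.

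**Step 1: the plan's own figure.** Half-width = 1.96 × √(p(1−p)/n) with n = 90 (Section 13.1).

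- p = 0.80: 1.96 × √(0.80 × 0.20 / 90) = 8.26 points (stated 8.3).
- p = 0.88: 1.96 × √(0.88 × 0.12 / 90) = 6.71 points (stated 6.7).

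The stated precision reproduces, and nothing here disputes it.

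**Step 2: how far follow-up reaches under 7.2.** Assume the 4 months run from the last dose, so end of follow-up = last-dose month + 4.

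| Last dose (month) | Follow-up ends (month) | Reaches Month 6? | Reaches Month 12? |
|---|---|---|---|
| 0 | 4 | no | no |
| 1 | 5 | no | no |
| 2 | 6 | yes, just | no |
| 3 to 7 | 7 to 11 | yes | no |
| 8 | 12 | yes | yes, just |
| 9 to 11 | 13 to 15 | yes | yes |

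Month 6 relapse status is lost for 2 of 12 last-dose times and Month 12 status for 8 of 12, in subjects with no relapse recorded by then. If the 4 months ran instead from the first withheld monthly dose (last dose + 1 + 4), the counts would be 1 of 12 (baseline) and 7 of 12 (baseline to Month 6). These are counts of dose times, not of subjects: the documents do not say when subjects are expected to stop.

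**Step 3: MRI.** Under 7.2 a subject who stops before the Month 6 scan has neither the Month 6 nor the Month 12 scan called for. One who stops between the two loses the Month 12 scan. This holds whether or not relapse follow-up reaches those months.

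**Step 4: which analyses are touched.**

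- Protocol Kaplan-Meier estimates (13.4.1, 13.5.1): a shortened subject is censored when follow-up ends. Earlier time still counts, but the later part rests on censoring being unrelated to relapse.
- Protocol ARR (13.5.1): person-time after the cut-off is missing.
- Protocol 12-month McNemar test: the subject is excluded.
- Protocol MRI counts: missing and generally not imputed.
- SAP study-period ARR: SAP Section 4.1 ends the study period at the last visit, so its length depends on which follow-up rule the site applied.
- SAP primary analysis (5.1): unchanged, because a relapse-free discontinuer is censored at the last dosing date however long follow-up lasts.

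**The case against.** The strongest reply is that this is ambiguity, not contradiction. Section 7.2 does not say that follow-up is limited to 4 months, and 9.2 speaks of missed doses, not of permanent discontinuation. Footnote 14 already separates leaving the study from stopping drug. The 4 months are not empty either: 7.2 collects relapses throughout, and 10.5.1 asks for serum transaminases up to 4 months after the last dose. This stands, and it is why the point is one of reconciliation. It does not tell a site which visits continue.

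Four stronger readings are tempting, and the documents do not support them.

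- *Section 9.3 forces out anyone who stops daclizumab.* It does not. The nearest reason is "The subject is unwilling or unable to comply with the protocol", and a subject taken off drug under 10.5.1 is following the protocol. A site could misread it, which justifies a cross-reference and no more.
- *The primary result is seriously exposed.* Under the protocol's analysis, Month 6 status is lost only for the earliest stoppers. Under the SAP's, later follow-up does not enter. Whether SAP censoring at the last dose is informative is a separate question.
- *Missing outcomes outweigh the planned precision.* If all 10 of 100 assumed drop-outs were lost, an observed 80% among 90 would be compatible with 72.0% (72/100) to 82.0% (82/100), and 88% with 79.2% to 89.2%. That 10-point span is a full range, so it belongs beside the full interval widths of 16.6 and 13.4 points (2 × 8.3 and 2 × 6.7), which are larger. Only if all ten relapsed would the downward shift (8.0 or 8.8 points) be close to or above the half-width. Section 13.1 also does not say that its drop-outs are early drug stoppers.
- *Stoppers are the subjects most likely to relapse.* Section 5.2.1 places recurrence in the first 6 months for natalizumab switchers generally. It says nothing specific about those who stop daclizumab.

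**Conclusion.** The point holds as an unreconciled follow-up rule that should be fixed. Sections 7.2 and 4.2 give discontinuers 4 months and merge two different events, 9.2 continues follow-up without limit, and 13.2 keeps these subjects in the analysis. The main exposure is Month 12 relapse status (8 of 12 last-dose times) and MRI after stopping; Month 6 relapse status is exposed for 2 of 12. These counts assume that 4 months is the end of follow-up and that it runs from the last dose. The resulting bias cannot be sized, because the documents give neither the timing of discontinuation nor the relapse risk after it.

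Practical weight is reduced. The SAP records termination at about 30 subjects, plans an abbreviated report, and no longer analyses the permanent discontinuation rate. What remains affected in the SAP is the study-period ARR and the reading of per-visit MRI summaries.

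**What to change.** Reconcile Sections 4.2, 7.2, 9.2 and 9.3:

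1. State in 4.2 and 7.2 that stopping daclizumab is not study withdrawal. Such subjects stay on the Table 1 relapse visits and MRIs through Month 12, and have the 4-month safety contact as well if it falls later.
2. Make 9.2 say the same for permanent discontinuation as for missed doses.
3. Add a cross-reference in 9.3 so that stopping drug is not read as a reason for study withdrawal. The reasons for stopping treatment are outside this point and need no change.
4. Use the early discontinuation visit only for subjects who leave the study, as footnote 14 already defines it.

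For the abbreviated report, state which follow-up rule was applied and list, for each discontinuer, the last dose date and the last relapse and MRI assessments. State also that study-period ARR depends on that rule.

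The cost is protocol wording, one listing, and some visits and scans by subjects who are off drug. The visits are already in Table 1.

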### **7.3. Early Termination of Study**

Biogen may terminate this study at any time, after informing the Investigator(s). Biogen will notify the Investigators if the study is placed on hold, completed, or closed.

CONFIDENTIAL

The information contained herein may not be used, disclosed, or published without the written consent of Biogen MA Inc.

## 8. STUDY POPULATION

### 8.1. Inclusion Criteria

To be eligible to participate in this study, candidates must meet the following eligibility criteria during the screening period (28 days [+3 days] following the last dose of natalizumab):

1. Ability to understand the purpose and risks of the study and provide signed and dated informed consent and authorization to use protected health information (PHI) in accordance with national and local subject privacy regulations.
2. Aged 18 to 55 years old, inclusive, at the time of informed consent.
3. Must have documented diagnosis of RRMS (McDonald 2010 Criteria) at screening [Polman 2011].
4. Must have been treated with natalizumab for at least the 12 months prior to screening and have not missed 2 or more consecutive scheduled doses.
5. Must be naïve to daclizumab and other forms of daclizumab such as Zenapax® prior to enrollment.
6. Must have a confirmed EDSS score of 0 to 5.5, inclusive, at screening.
7. Female subjects of childbearing potential must practice effective contraception from Day -1 and be willing and able to continue contraception for duration of the study.

### 8.2. Exclusion Criteria

Candidates will be excluded from study entry if any of the following exclusion criteria exist during the screening period (28 days [+3 days] following the last dose of natalizumab):

1. Inability to comply with study requirements or, at the discretion of the Investigator, is deemed unsuitable for study participation.
2. Current participation in another investigational study.
3. Diagnosis of primary progressive, secondary progressive, or progressive relapsing MS (as defined by Lublin and Reingold) [Lublin 2014].
4. Females breastfeeding, pregnant, or planning to become pregnant; or women who have a positive pregnancy test result during screening.
5. History of drug or alcohol abuse (as defined by the Investigator) within 1 year prior to screening.
6. History of severe opportunistic infections (including PML) or any clinically significant, cardiac, endocrinologic, hematologic, hepatic, immunologic, metabolic, urologic, pulmonary, neurologic (other than MS), dermatologic, psychiatric, and renal, or other major disease, as determined by the Investigator.
7. Discontinued natalizumab due to suspicion of PML.

CONFIDENTIAL

The information contained herein may not be used, disclosed, or published without the written consent of Biogen MA Inc.

8. Known active malignancies (subjects with cutaneous basal cell carcinoma that has been completely excised prior to study entry remain eligible).
9. Clinically significant lab abnormalities revealed by blood tests at screening apart from those known to be associated with natalizumab (e.g., lymphocytosis).
10. Pre-existing hepatic disease or hepatic impairment, including ALT or AST at least 2 times the ULN (normal range for AST: 8 to 48 units per liter and for ALT: 7 to 55 units per liter). The normal range for liver enzyme levels may vary slightly by laboratory.
11. A history of autoimmune hepatitis or other autoimmune condition involving the liver.
12. The subject is using another MS therapy concomitantly.
13. Known history of human immunodeficiency virus (HIV).
14. Positive test result for Hepatitis C virus (test for hepatitis C virus antibody [HCV Ab]) or hepatitis B virus (test for hepatitis B surface antigen [HBsAg] and/or hepatitis B core antibody [HBcAb]). History of transplantation or any anti-rejection therapy.
15. Have had evidence of disease activity within the 6 months prior to screening visit defined as the following:
  - MS relapse, or
  - Gd+ enhancing lesions, or new or enlarging T2 lesions over the last 6 months, or
  - Disease progression (any increase of EDSS in the past 6 months).
16. The subject is considered by the Investigator to be immunocompromised based on medical history, physical examination, or laboratory testing.
17. The subject has been treated with immunosuppressive or immunomodulating treatments including mitoxantrone, azathioprine, methotrexate, cyclophosphamide, or mycophenolate mofetil.

CONFIDENTIAL

The information contained herein may not be used, disclosed, or published without the written consent of  
Biogen MA Inc.

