**Table 1: Study Schedule of Assessments**

Study Period	Screening		Study Follow-up							
Visit Number	1	2	3	4	5	6	7	8	9	10
Title	Enrollment (Day - [28+3] to -1)	Baseline (Day 0)	Month 1 (± 4 days)	Month 3 (± 4 days)	Month 4 (± 4 days)	Month 6 (± 4 days)	Month 9 (± 4 days)	Month 12 (± 4 days)	Month 15 Safety follow-up  (± 14 days)	Early discontinuation 
Informed consent 	X									
Inclusion/exclusion criteria	X									
Demographics	X									
Disease and medical history	X									
MS treatment history	X									
MRI 	X		X		X	X		X		
Pregnancy testing 	Monitor and record throughout the study									
Liver function testing (AST/ALT) 	X		X	X	X	X	X	X	X 	X
Concomitant medications and non-drug therapies	Monitor and record throughout the study									
██████████	X	X		X		X	X	X		X
Vital signs	X	X	X	X		X	X	X		X
Physical examination	X	X	X	X		X	X	X		X
██████████	X	X	X	X		X				
MS relapse assessment		X	X	X		X	X	X	X	X
Daclizumab dispensation/ administration 		X	X	X	X	X	X			

CONFIDENTIAL

The information contained herein may not be used, disclosed, or published without the written consent of Biogen MA Inc.

Study Period	Screening		Study Follow-up							
Visit Number	1	2	3	4	5	6	7	8	9	10
Title	Enrollment (Day - [28+3] to -1)	Baseline (Day 0)	Month 1 (± 4 days)	Month 3 (± 4 days)	Month 4 (± 4 days)	Month 6 (± 4 days)	Month 9 (± 4 days)	Month 12 (± 4 days)	Month 15 Safety follow-up  (± 14 days)	Early discontinuation 
Daclizumab dosing diary 						X	X			
Daclizumab accountability	Monitor and record throughout the study									
Hematology (CBC) 		X	X	X		X	X	X		X
Blood chemistry 		X	X	X		X	X	X		X
		X	X	X		X	X	X		
		X				X		X		
		X	X	X		X	X	X		
AEs/SAEs	Monitor and record throughout the study									

**Abbreviations:** MS: Multiple Sclerosis; MRI: magnetic resonance imaging; [REDACTED]; CBC: complete blood count; ALT: alanine transaminase; AST: aspartate transaminase; NK: natural killer T-cells; [REDACTED]; AE: adverse event; SAE: serious adverse event.

CONFIDENTIAL

The information contained herein may not be used, disclosed, or published without the written consent of Biogen MA Inc.

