## Efficacy and Safety of Daclizumab in Subjects with RRMS Switching from Natalizumab

1. Written informed consent must be obtained prior to start of the study.
2. Screening MRI should occur no later than 7 days prior to the first dose of daclizumab. For subsequent visits, MRI scan can be performed up to 4 days prior to the visit. Ad-hoc MRIs may be conducted as needed, such as in the event of a relapse to rule out PML diagnosis.
3. This is required only for females of child-bearing potential. A urine pregnancy test will be performed monthly.
4. Liver function tests (LFTs) are required to be performed monthly (either on-site or via home visits at Month 7, 8, 10 and 11, if applicable), and samples will be analyzed centrally for the purposes of this study. Results from either local or central LFT tests can be used for medical management of the patient and to determine whether dosing should continue or be suspended at the monthly dosing timepoint. In cases where local LFTs were performed, samples must also be collected for central analysis.
5. Liver function tests (LFTs) during the safety follow-up will be performed only if the subject is continuing daclizumab or if the subject is within 4 months since study treatment discontinuation, and monitoring is deemed appropriate by the Investigator; Abnormal AST/ALT values as described in the product label will lead to treatment suspension or discontinuation.
6. [REDACTED]
7. Samples will be analyzed centrally.
8. Daclizumab dosing will start at baseline and occur monthly until Month 11. Doses at baseline and Months 1, 2, 3, 4, 5, 6 and 9 will be administered in the clinic, and doses at Months 7, 8, 10 and 11 can be administered at home or in the clinic. Daclizumab dosing will not begin until a minimum of 28 days have passed since last natalizumab dose. Before a monthly dose of daclizumab is given, LFT results from a prior test performed within the previous 28 (+3) days must be reviewed by the Study Neurologist or their backup.
9. Subjects will be provided a dosing diary at the Month 6 and Month 9 visits to record observations for home dosing only; home dosing is possible for Month 7, 8, 10, and 11. A window of  $\pm 4$  days applies to daclizumab dose even if it is done at home; subjects should be appropriately instructed on daclizumab self-administration using the autoinjector.

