10. Blood chemistry assessments will include bilirubin testing at baseline. Bilirubin testing must also be done if ALT/SGPT, or AST/SGOT  $>3*ULN$ , since treatment must be permanently discontinued with the concomitant elevation of total bilirubin  $>2*ULN$ .
11. [REDACTED]
12. [REDACTED]
13. Safety assessment follow-up at 4 months after last study treatment dose.
14. Early study discontinuation is discontinuing study participation at any time after baseline.

CONFIDENTIAL

The information contained herein may not be used, disclosed, or published without the written consent of Biogen MA Inc.

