### **9.1. Screening, Enrollment and Randomization**

Subjects must be consented before any screening tests or assessments are performed. At the time of consent, the subject will be enrolled into the study.

Subjects will be initiated on daclizumab after all screening assessments have been completed and after the Investigator has verified that they are eligible per criteria in Sections 8.1 and 8.2. No subject may begin treatment prior to registration and assignment of a unique subject identification number. Any subject identification numbers that are assigned will not be reused even if the subject does not receive treatment. If an eligible subject was approached and did not participate in the study, the reason for nonparticipation will be documented in the screening log

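### As scheduled, exclusion 9 cannot be applied before the first dose to the CBC, or to chemistry other than AST/ALT and bilirubin

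*Protocol*

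**What the plan says.** **The criterion.** Exclusion 9 in Protocol Section 8.2 reads: "Clinically significant lab abnormalities revealed by blood tests at screening apart from those known to be associated with natalizumab (e.g., lymphocytosis". Its own example, lymphocytosis, is a blood count finding, so haematology is within its scope. Exclusion 16 lets the Investigator judge a subject immunocompromised from history, examination or laboratory testing.

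**The schedule.** Section 4.2 states: "Blood chemistry and hematology assessments will be performed at baseline and at Months 1, 3, 6, 9 and 12". Table 1 agrees. The CBC and blood chemistry rows are legible, their Enrollment cells are empty, and the first mark is at Baseline, Day 0. Footnote 8 states: "Daclizumab dosing will start at baseline and occur monthly until Month 11".

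**The laboratory.** Footnote 7, attached to both rows, says that "samples will be analyzed centrally", and Section 16.1.3 confirms it for haematology and chemistry. Footnote 4 and Section 11.3.2 allow local results for liver function tests. No such allowance is made for the CBC or the rest of the chemistry panel.

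**The eligibility step.** Section 9.1 says "Subjects will be initiated on daclizumab after all screening assessments have been completed" and only once the Investigator has verified eligibility. Table 1 marks the inclusion/exclusion check at Enrollment only.

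**Bilirubin.** Section 4.2: "Bilirubin testing must be done together with the first AST/ALT test at the enrollment visit". Footnote 10: "Blood chemistry assessments will include bilirubin testing at baseline". Section 10.5.1 requires a level before treatment starts.

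**The concern.** An exclusion that depends on blood results works only if the results can be read before treatment. Here the blood count and most of the chemistry panel are first drawn at the visit where the first injection is given, and the tubes go to a central laboratory. A site that keeps to the visit schedule has no scheduled result for these tests when it decides on eligibility.

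What is at stake is subject safety and a clean eligibility record. A subject with, for example, marked cytopenia on Day 0 could be dosed and found ineligible afterwards. That subject would remain in the full analysis set, because SAP Section 3 requires only one dose.

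**Working it through.** No sample size, error rate or other statistical figure is involved, so there is no planned number to reproduce. The check compares the day of each draw with the day of the first dose.

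**Inputs**
- Enrollment window: Day -[28+3] to Day -1 (Table 1), and 28 + 3 = 31, so Day -31 to Day -1.
- Baseline visit: Day 0, with no visit window shown (Table 1).
- First dose: Baseline, so Day 0 (Table 1 footnote 8).
- Central laboratory turnaround: not stated.

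**Formula:** lead time = day of first dose minus day of first scheduled draw.

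| Test | First scheduled draw | Lead time | Pre-dose review stated? |
|---|---|---|---|
| AST/ALT | Enrollment | 0 - (-1) = 1 day to 0 - (-31) = 31 days | Yes (footnote 8, Section 11.3.2) |
| Bilirubin | Enrollment (Section 4.2) | 1 to 31 days | Level required before treatment (Section 10.5.1) |
| CBC | Baseline, Day 0 | 0 - 0 = 0 days | No |
| Chemistry other than the above | Baseline, Day 0 | 0 - 0 = 0 days | No |

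Hepatitis B and C tests also appear in the Section 11.2.1 enrollment list, so they count as screening tests.

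**Reading the table.** With a lead time of 0 days, a central result arrives before the injection only if turnaround is same-day and the site waits for it. The documents state neither. Any turnaround of one day or more puts the result after the first dose. Section 11.1 says that haematology and chemistry data are sent to sites and reviewed by the Study Neurologist, but it does not place that review before the first dose. The protocol does give pre-dose instructions elsewhere: for liver function tests, and for vital signs (Section 11.3.4).

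**What this leaves of exclusion 9.** It can act before dosing on AST/ALT, bilirubin and hepatitis serology. AST/ALT and hepatitis already have their own exclusions (10 and 14). Blood counts and general chemistry, which neither of those exclusions covers, have no scheduled pre-dose result.

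**Size.** The schedule applies to every dosed subject. The number dosed with a disqualifying value is N × p, and p is not given in the documents. Each percentage point of p corresponds to 100 × 0.01 = 1 subject in the planned sample, or 30 × 0.01 = 0.3 of the approximately 30 enrolled (SAP Section 4). This is scaling only, not an estimate. Because Section 9.1 counts a subject as enrolled at consent, the number dosed may be below 30.

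**The case against.** **Day 0 may belong to screening, and Section 9.1 already bars dosing until eligibility is verified.** The Table 1 header, as extracted, appears to place Visits 1 and 2 under Screening, and Section 11.3.1 foresees subjects found ineligible at baseline. So the protocol does not order sites to dose before eligibility is known. This stands as a reading of the words. It does not produce a result before the injection, and it leaves the site with a safeguard that the schedule does not support for these tests.

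**Other criteria cover some of the ground.** Exclusion 6 removes known clinically significant haematologic, immunologic, metabolic and renal disease. That is true, but it rests on history. A laboratory exclusion is there to find what history does not show.

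**Section 11.2.1 is weak evidence.** Its list also omits AST/ALT, bilirubin and MRI, which Section 4.2 requires at enrollment. This is right: the absence of CBC and chemistry from that list proves little, and the point rests on Section 4.2 and Table 1.

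**Redaction.** Some Table 1 rows, laboratory items and footnotes are blacked out, so the enrollment blood panel cannot be fully listed. The CBC and chemistry rows themselves are legible.

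**Stronger readings a reader might infer, which the documents do not support**
- *Exclusion 9 cannot be applied at all.* It can act on the enrollment tests listed in the working.
- *The bilirubin statements contradict each other.* An enrollment test plus a baseline test satisfies Section 4.2, footnote 10 and Section 10.5.1 together. Footnote 10 does not say that the baseline test is the first or only one. Raised bilirubin is therefore not a good example of the gap.
- *Exclusion 16 fails too.* Its history and examination grounds are alternatives and still work. Only its laboratory ground shares the timing gap.

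**Conclusion.** The point holds for blood counts and for chemistry other than AST/ALT and bilirubin: exclusion 9 has no scheduled result for them before the first dose. The lead time is 0 days for every subject dosed under the schedule, against 1 to 31 days for AST/ALT. The conclusion assumes that central results are not available on the day of the draw. The documents give no turnaround time and no instruction to wait.

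The matter is one of safety eligibility and internal consistency. The documents do not show how many subjects, if any, were wrongly dosed, and no effect on the primary endpoint follows from them.

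A reader might also infer that the gap distorts the haematology abnormality table in SAP Section 5.4.2. It is true that this table is not expressly limited to post-baseline values. But SAP Section 4.3 allows a value from the first dosing date to serve as baseline, and Protocol Section 13.5.2.4 plans shifts from baseline, so an abnormality already present on Day 0 can be identified. Whether the table counts Day 0 values is a separate question, which moving the eligibility draw would not settle.

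**What to change.** Reconcile exclusion 9, Section 4.2, Table 1 with footnote 7, and Section 9.1, as follows:

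1. In Section 4.2 and Table 1, add CBC and blood chemistry at Enrollment, on the blood draw already taken there for AST/ALT and bilirubin.
2. List both in Section 11.2.1.
3. Mark in Table 1 an eligibility confirmation made from those results before the first dose. This also closes the laboratory part of exclusion 16.
4. Keep the Day 0 draw as the analysis baseline.
5. Optionally, clarify in footnote 10 that the baseline bilirubin is in addition to the enrollment test.

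**Cost.** Protocol wording, one extra tube and one extra central panel per screened subject, and possibly a few more screen failures. No new visit or venepuncture is needed. SAP Section 2 records that the trial has been terminated, so the change cannot alter what was done for subjects already dosed. It matters if this schedule is reused.
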